20.0 Compensation for Research-Related Injury

20.1 If the participant needs medical care because of taking part in this research study, contact the investigator and medical care will be made available. Generally, this care will be billed to the participant's insurance, or other third party. Florida State University has no program to pay for medical care for research-related injury.

21.0 Economic Burden to Subjects

21.1 There are no anticipated costs that subjects may be responsible for due to participation in the research.

22.0 Consent Process

22.1 Indicate whether you will you be obtaining consent, and if so describe:

- Consent will take place within the ISSM research laboratory.
- The prospective participant may take as long as they would care to between being informed and signing the informed consent. This is completely up to their discretion.
- Ongoing consent will be ensured via weekly check-ins with regard to their adherence to the supplementation protocol.
- Yes, we will follow “SOP: Informed Consent Process for Research (HRP-090).”
 - Only the trained PI or a co-investigator will be permitted to lead the informed consent process with the potential participant.
 - The discussion of informed consent will take as long as is needed for the potential participant to feel informed and comfortable about their voluntary participation in this research.
 - We will emphasize that this is completely voluntary and that the participant is able to refuse or withdraw from the study at any time.
 - To ensure the subjects’ understanding, we will ask the participants to repeat back to us the perceived risks and benefits.
 - The informed consent document will be at a 10th grade reading level, however as previously mentioned all topics will be read to the participants and explained.

Non-English Speaking Subjects

- There are no current indications that our subjects will not speak English. If a potential participant would like to take part in the study and meets the inclusion criteria appropriate accommodations will be made to ensure their consent is informed in their language. Accommodations will include a non-English consent form.
- N/A
- N/A

Waiver or Alteration of Consent Process (consent will not be obtained, required information will not be disclosed, or the research involves deception)

- Review the “CHECKLIST: Waiver or Alteration of Consent Process (HRP-410)” to ensure you have provided sufficient information for the IRB to make these determinations.

Subjects who are not yet adults (infants, children, teenagers)

- N/A

Cognitively Impaired Adults

- N/A

Adults Unable to Consent

- N/A

Adults Unable to Consent

- N/A

23.0 Process to Document Consent in Writing

23.1 Yes, the “SOP: Written Documentation of Consent (HRP-091)” will be followed.

23.2 N/A

23.3 Please see the attached Informed Consent Document

24.0 Setting

24.1 *Describe the sites or locations where your research team will conduct the research.*

- Participants will be recruited from the general population of Tallahassee, FL and surrounding rural areas within reasonable commuting distances. Participants will be recruited via public service announcements, social media, and flyers posted on campus, in health clinics and fitness centers, and in employment development centers.
- Research will be conducted with the Institute of Sport Sciences and Medicine (ISSM) on FSU’s main Tallahassee campus.
- N/A
- *For research conducted outside of the organization and its affiliates describe:*
 - N/A

25.0 Resources Available

- Between various recruitment locations mentioned, we anticipate an ample amount (>50) of eligible subjects. As the power analysis revealed a required sample size of 30, the PI does not anticipate any issues regarding recruitment.
- The PI aims to complete data collection no later than Spring 2026 and complete data analysis and writing no later than Summer 2026.
- The ISSM is a well-funded, fully stocked human performance laboratory. It has all the equipment and space needed to fully support this research. The facilities are more than satisfactory for the completion of this study.
- First Aid, automated external defibrillator (AED), fire extinguishers, and showers are available at each location. All data collection visits will be attended by CPR-trained staff. Although unlikely, any medical needs beyond the scope of first aid will consist of a researcher escorting the participant to the FSU medical center on campus.
- The PI will have several meetings with each person in the research team going over each individual role. This will help ensure that each member of the research team is adequately informed about the protocol, the research procedures, and their duties and functions.

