primarily to genotype – a known confounder (41). The American College of Sports Medicine’s classifications of training status (i.e., <150 minutes of moderate-intensity and/or <75 minutes of vigorous aerobic exercise per week for the last 3 months) as well as normative $\text{VO}_{2\text{max}}$ values will be used to dichotomize the groups with the fit (and chronically-trained) and unfit (and sedentary) group having values in the upper and lower quartiles (i.e., $\geq 75^{\text{th}}$ percentile and $\leq 25^{\text{th}}$ percentile) for their age and sex, respectively (42). This equates to a $\text{VO}_{2\text{max}}$ value of ≥ 55.2 and 44.7 ml/kg/min for fit males and females, respectively, and ≤ 40.1 and 30.5 ml/kg/min for unfit males and females, respectively. Participants will then be provided with a wearable, wrist-worn sleep and cardio-autonomic function monitor, to be worn on the non-dominant wrist throughout the entirety of the project timeline, including a two-week initialization period to establish baseline sleep cardio-autonomic data. This initialization period will take place following consent and prior to the first data collection visit. Next, participants will then be familiarized with daily sleep, physical activity, and 3-day nutrition logs as well as a PVT smart phone application, all of which will be performed throughout the study. Lastly, participants will be assessed for sleep chronotype via a morningness-eveningness questionnaire to inform any potential differences in sleep intervention response post hoc. Following the initialization period, participants will be randomly assigned to either a normal or partial sleep deprivation intervention, both of which will last 4 days. The partial sleep deprivation intervention will consist of prescribed bed and wake times eliciting a 30% reduction in habitual time in bed, identical to a protocol utilized by Roberts, et al. (43). Following the first sleep intervention period, participants will again report to the ISSM for the first of four data collection visits (i.e., Post-Test 1). Data collection will consist of assessment of central hemodynamics, cardio-autonomic function, physical and cognitive performance, as well as overall health. Participants will then undergo a 7-day washout/ post-intervention observation period, in which they will continue to track and log their sleep and perform daily PVT to allow for recovery evaluation in those metrics, prior to crossing over to the other sleep intervention. During the washout period, participants will also return to the lab to repeat the blood work and CMJ testing to allow for recovery assessment in those values (i.e., immediate post-intervention vs 3-day post-intervention values; Recovery 1). Following completion of the washout/observation period, participants will crossover to the other sleep intervention and repeat the testing protocols (i.e., Post-Test and Recovery 2). Data collection visits will occur at the same approximate time of day for each individual to account for diurnal patterns in the data collected. In total, the protocol will last approximately 5 weeks and consist of 5 visits.

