
6.2 Research Procedures

Initial Visit: All data collection time points are outlined in Figure 1 below. Prior to participation, voluntary consent to participate will be obtained. Eligible participants (i.e., those deemed fit to participate via the Physical Activity Readiness Questionnaire [PAR-Q+] in conjunction with the American College of Sports Medicine guidelines for physical activity) will then complete a questionnaire to establish typical training characteristics (i.e., frequency, intensity, time, type, and history). Specifically, the PAR-Q+ screens individuals for signs or symptoms of cardiovascular, metabolic, and or renal disease which would make it inadvisable for them to participate in physical activity. Individuals who are not deemed fit to participate, according to the PAR-Q+, will not be allowed to continue with participation. They will then be assessed for body composition (Bod Pod; Cosmed, Chicago, IL) prior to performing a maximal treadmill test (protocol described below) to determine maximal oxygen consumption capacity (VO_{2max}). In the case that an individual does not qualify for the study (i.e., those meeting requirements for training status and VO_{2max}), all data collected on that individual will be destroyed. Individuals who do qualify will be provided with a WHOOP (Boston, MA) wearable, wrist-worn multi-sensory biometric and cardio-autonomic function monitor. The WHOOP band will be worn on the non-dominant wrist throughout the entirety of the project timeline (~1.5 months), including a two-week initialization period prior to the first data collection visit. Participants will then be familiarized with daily sleep, physical activity, and 3-day nutrition logs as well as a PVT smart phone application, all of which will be performed throughout the study. Specifically, participants will complete the sleep and physical activity logs and PVT task daily throughout the enrollment period, while they will complete the 3-day nutrition log in the 3 days immediately prior to Post Test 1 and 2 visits (described in detail below). Lastly, participants will be assessed for sleep chronotype via a morningness-eveningness questionnaire to inform any potential differences in sleep intervention response post hoc.

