VO_{2max} Testing Protocol: Testing will take place on a motorized treadmill (Woodway USA, Waukesha, WI). Oxygen consumption will be measured via a Parvomedics TrueOne 2400 metabolic cart (Salt Lake City, UT). Each testing stage will last for two minutes, and heart rate (HR) and rating of perceived exertion (RPE) will be recorded in the last 15-20" of each stage. The participant will begin at a speed of 3 miles per hour for the warm-up stage. Upon completion of the warm-up the speed will be increased to 5 miles per hour. The speed will be increased by 1.5 miles per hour for each successive stage until an RPE of 13 or greater is achieved. Following this, the speed will remain constant for the remainder of the test. For the following stage, the grade of the treadmill will increase to 2%, and will be increased by an additional 2% for each subsequent stage until volitional exhaustion. Attainment of maximal oxygen consumption will be ensured by satisfying two of three criteria: plateau in oxygen consumption with increasing workload, respiratory exchange rate (RER) >1.1, or RPE >17. Standardized verbal encouragement will be provided throughout the test. Immediately after the test, participants will be given a three-minute cooldown period in which they will be asked to walk at 3 mph.

Sleep Intervention: Following the two-week initialization period, participants will be randomly assigned to either a normal or partial sleep deprivation intervention, both of which will last 4 days. The last week of the two-week initialization period will be used to

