Experimental Visits: Following the first sleep intervention period, participants will come in for the first of four data collection visits (i.e., Post-Test 1). Data collection visits will begin of the completion of the Pittsburgh Sleep Quality Index (PSQI) and Profile of Mood States (POMS) questionnaire to characterize sleep quality and psychological mood states, respectively. Next, central arterial pulse wave form analysis and pulse transit time (carotid-femoral PWV [cf-PWV]; via applanation tonometry) will be assessed using a SphygmoCor XCEL device (AtCor Medical, New South Wales, Australia), followed by a standard venipuncture procedure to allow for inflammatory marker characterization, total blood cell counting, as well as blood lipid and glucose profiling to account for known hemodynamic confounders (26). The venipuncture procedure will be performed by the primary investigator (certified phlebotomist trained; 5+ years of experience) following the attached standard operating procedure for venipuncture and will entail the collection of 10-30 mL of blood, as is typical of a standard blood venipuncture procedure. If the primary investigator is unavailable to perform the procedure or is unable to do so, the Clinical Research and Trials Unit will be utilized. Lastly, participants will perform a short countermovement jump (CMJ) test to quantify their reactive strength index (RSI).

Participants will then undergo a 7-day washout/ post-intervention observation period, in which they will continue to track and log their sleep and perform daily PVT to allow for recovery evaluation in those metrics, prior to crossing over to the other sleep intervention. During the washout period, participants will also return to the lab to repeat the blood work and CMJ testing to allow for recovery assessment in those values (i.e., immediate post-intervention vs 3-day post-intervention values; Recovery 1). Following completion of the washout/observation period, participants will be assigned to the other sleep intervention in a crossover fashion and complete the second 4-day intervention before returning for another data collection visit (i.e., Post Test 2) identical to Post Test 1. They will then enter another 7-day post-intervention observation period and performing a second recovery data collection visit (i.e., Recovery 2). Data collection visits will occur at the same

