approximate time of day for each individual to account for diurnal patterns in the data collected. In total, the protocol will last approximately 5 weeks and consist of 5 visits.

Central Hemodynamic Assessment: Participants will be assessed for central arterial pulse wave form and cf-PWV following both sleep interventions with re-analysis occurring 3 days later to quantify the response to, and recovery from, the two sleep interventions between the two groups. The central hemodynamic (i.e., central blood pressure, augmentation index [absolute and relative to a heart rate of 75 beats per minute], mean arterial pressure, and pulse pressure) and arterial stiffness (i.e., cf-PWV) variables of interest will be collected and analyzed following methods identical to those utilized by Grosicki, et al. (34).

Health and Well-Being Assessment: Both metrics of sleep quality and cardio-autonomic function (i.e., resting heart rate, heart rate variability, and a proprietary, WHOOP-generated recovery score) will be collected via the WHOOP devices. The wearing of the device throughout the entirety of the project timeline will allow for the quantification of these measures in response to, and recovery from, the two sleep interventions, which will be compared between the two groups. Further, data from the devices will be analyzed following protocols set forth by Greenwalt, et al. (44). Using blood samples collected during the venipuncture protocols performed at the four data collection visits, sleep intervention response and recovery levels of circulating plasma concentrations of pro- (CRP, IL-6, IL-1 β , and TNF- α) and anti-inflammatory (IL-10) cytokines will be assessed using protocols similar to that outlined by Smith, et al. (45). Additionally, portions of the blood samples will undergo hematologic analysis to characterize shifts in the composition of immune cells through methods similar to those of Schluter et al. (46). Finally, POMS data will be used to evaluate intervention-associated shifts in psychological mood states between the two groups following the methodology of Shacham (47).

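### Section 25 sends every medical need beyond first aid to the campus medical center by researcher escort, with no exception for the cardiac event that Section 15.1 foresees during maximal treadmill testing

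*Combined protocol and SAP*

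**What the plan says.** Section 25.0 lists first aid and an AED at each location. It then says "All data collection visits will be attended by CPR-trained staff". For anything more serious it gives one step: "any medical needs beyond the scope of first aid will consist of a researcher escorting the participant to the FSU medical center on campus".

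Section 15.1 names a cardiac event or injury as a possible risk of maximal treadmill testing. It puts the risk at 6 in 10,000 and says the testers are trained and have more than ten years' experience. Under the VO2max protocol in Section 6.2, the treadmill grade "will be increased by an additional 2% for each subsequent stage until volitional exhaustion". The test belongs to the Initial Visit, where body composition is measured "prior to performing a maximal treadmill test (protocol described below").

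Other safety text:
- **Section 6.2:** PAR-Q+ screening before the test; people not cleared do not continue.
- **Section 10.1:** exclusion of diagnosed cardiovascular disease, previous infarction and uncontrolled hypertension.
- **Section 15.4:** a specific response to needle sticks.
- **Section 18.1:** safety information collected at every study visit, harms evaluated during experimental visits, unanticipated adverse events recorded, and review by the research team with referral to an associate dean if needed.
- **Section 20.1:** an injured participant is to contact the investigator, and care will be made available.

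**The concern.** The escort sentence is written as a general rule, so it also governs the most serious foreseeable event. A participant who collapses, loses consciousness or has chest pain on the treadmill should not be walked across campus; help should come to the laboratory. A staff member following Section 25.0 literally would use first aid and the AED, and would then find only the escort as the next step. The protocol does write a specific response for a lesser hazard, the needle stick, so the lack of one for a cardiac event stands out.

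The test is run to exhaustion in sedentary as well as trained volunteers. Because it is also the fitness screen, some people who take it will never be enrolled. Participant safety is at stake here, not inference.

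A smaller, related point is that the CPR sentence is tied to a phrase that Section 6 uses for the four post-intervention and recovery visits, and the maximal test happens before any of them.

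**Working it through.** The main point rests on the text. The arithmetic gives a visit count and a sense of scale.

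**1. Escalation.** The provisions that could apply to a cardiac event during the test are:
- Section 25.0: first aid, AED and CPR-trained staff, then the escort.
- Section 15.1: experienced testers, with no response step.
- Section 18.1: collection, recording and review of safety information, with no immediate response step.
- Section 20.1: contact with the investigator, with no emergency step.

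None has staff call emergency services. The escort is the only written action after first aid, AED and CPR.

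**2. Visit count for the CPR sentence.**
- Total visits, Section 6.2: "the protocol will last approximately 5 weeks and consist of 5 visits".
- Data collection visits, Section 6.2: after the first sleep period "participants will come in for the first of four data collection visits (i.e., Post-Test 1"). The four are Post-Test 1, Recovery 1, Post-Test 2 and Recovery 2.
- Order, Section 6.1, on the two-week run-in: "This initialization period will take place following consent and prior to the first data collection visit".
- Remainder: 5 − 4 = 1, the Initial Visit, where the maximal test is done.

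On Section 6's count, the CPR sentence does not clearly reach the Initial Visit.

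**3. Scale.** Section 15.1 does not say whether 6 in 10,000 is per test, nor does it define the event. Assume a per-test probability p = 0.0006 for any event and independent tests. Then the expected number is n × p, and P(at least one) = 1 − (1 − p)^n.

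| Tests n | Basis | Expected events | P(at least one) |
|---|---|---|---|
| 30 | target, Section 12.1 | 30 × 0.0006 = 0.0180 | 1 − 0.9994^30 = 1.78% |
| 36 | recruitment ceiling, Section 12.2 | 36 × 0.0006 = 0.0216 | 1 − 0.9994^36 = 2.14% |
| 72 | 36 / 0.50, assuming half of those tested qualify | 72 × 0.0006 = 0.0432 | 1 − 0.9994^72 = 4.23% |

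The last row is there because qualification follows the test. Section 6.2 provides for this: "In the case that an individual does not qualify for the study", that person's data are destroyed. The 50% rate is an assumption. All rows count any event, and not every event would need an ambulance.

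**The case against.** The strongest reply is that the plan is already reasonably protected. Volunteers are aged 18 to 39, screened with the PAR-Q+ and excluded for known cardiovascular disease. The testers are experienced, and the AED and first aid provision is not limited by visit type. The escort sentence does not forbid an emergency call, and competent staff would make one. A laboratory procedure may exist in material that was not supplied, and the consent document was removed before review. All of this stands. It lowers the probability of harm and the likelihood that staff would follow the sentence literally. It does not make an escort the right instruction for a collapse, and Section 25.0 cites no other procedure.

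Two stronger readings are tempting, and the documents do not support either.

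- **That no CPR-trained person will be present at the maximal test.** Section 25.0 does not refer back to Section 6's count of four. Section 6.2 itself speaks of data collection time points under the Initial Visit heading, and Figure 1 is not shown. In ordinary usage, a visit that records body composition and VO2max collects data. The same team may attend every visit. This is an ambiguity of wording, not a demonstrated lack of cover.
- **That the plan does nothing about safety events except record them.** Section 18.1 also provides for collection at every study visit, evaluation of harms and review. What is missing is narrower: an immediate escalation step.

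**Conclusion.** The concern holds for the escort sentence. As written, it assigns the wrong step to a cardiac event that the protocol itself foresees, and nothing in the supplied text directs staff to call emergency services. It should be changed. Confidence is medium, because an emergency procedure may exist outside the supplied text.

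The CPR wording is secondary and merits only a clarification.

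The probability is low: about 2% for at least one event of any kind in 36 tests, if 6 in 10,000 is a per-test rate. This figure is for scale only and does not estimate emergencies that need escalation. The case for acting rests on the seriousness of the event and the small cost of the change. No endpoint, sample size or analysis is affected.

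**What to change.** Replace the escort sentence in Section 25.0 with:

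*For collapse, loss of consciousness, chest pain or any suspected cardiac event, staff will stop the test, call emergency medical services at once, start CPR and use the AED where indicated, and keep the participant in the laboratory until help arrives. Escort to the FSU medical center is for non-urgent needs only.*

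The trigger symptoms are proposed here and do not come from the documents. If a laboratory emergency procedure already exists, cite it and align the sentence with it.

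As a clarification, change the start of the CPR sentence so that it covers *all study visits, including the Initial Visit*.

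The cost is one replaced sentence, one changed phrase and a short briefing at the role meetings already planned in Section 25.0. No new equipment is needed. No staff are added if the same CPR-trained team runs all visits (assumption). Otherwise one trained person must attend each Initial Visit: at least 36 if 36 people are recruited, and more if some who are tested do not qualify.
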